We will be monitoring for safety of participants throughout the study. At the beginning of each therapy session, there will be a verbal check-in period in which patients can discuss any worsening of symptoms, or any suicidal ideation. In addition, in case of worsening of symptoms between sessions, the participant will be provided with the PI's direct [contact]), in addition to the telephone number for his/her therapist and other study personnel, and the participant will be encouraged to call.

On check-in or upon receiving a phone call from the participant, if the participant is found to have worsening of physical medical symptoms (e.g., pain), the patient's primary care provider will be contacted, and a close follow-up appointment will be obtained for the participant. In the event of worsening psychiatric symptoms (e.g., depression, anxiety), the patient may be referred to their mental health provider, or a referral may be placed to the Geriatric Psychiatry Outpatient Program in the even the participant does not have a primary mental health provider. In the event of suicidal or violent ideation, the participant will be referred immediately to the emergency department or to 911, as outlined in our suicide safety plan below.

In the event of worsening physical or medical symptoms, study procedures (i.e., psychotherapy) will be suspended after a conversation with the participant, if that is the

participant's preference. In the event of suicidal or violent ideation, study procedures (i.e., psychotherapy) will be suspended immediately.

Suicide Safety Plan:

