We do not expect any study participants to develop suicidal ideation in this treatment study for chronic pain. However, it is known that chronic pain patients have twice the rate of suicide of those without chronic pain. Therefore, we have a suicide safety plan in place. Research physicians and the research psychologist are clinicians in geriatric psychiatry, and each session will begin with a verbal check-in period, and assessments will be completed periodically to monitor for depression. If researchers feel that the participant is at risk for suicide and/or a threat to others while he/she is present at WLA either undergoing clinical interview, completion of assessments, therapy sessions, or other study procedures, he/she will be evaluated by a trained research physician or psychologist who is a study team member and brought to the WLA ER if psychiatric hospitalization is thought to be required. All Veterans will have the PI's direct [contact]) to call in the event of worsening symptoms and will also be instructed to dial 911 or report to the nearest ER if a psychiatric emergency, such as suicidal or violent ideation, occurs during the study but while the Veteran is not present at WLA. If a Veteran participant is noted to have significant depression but is not suicidal, the research team will discuss the benefits of treatment and provide contact information for the GLA Geriatric Psychiatry Outpatient Program.

Potential Benefits:

The study will be of direct relevance and benefit to older Veterans who suffer from chronic pain. All study participants will receive a psychological intervention, either standard treatment (CBT) or a promising experimental treatment (EAET). We anticipate this could be of benefit for participants on pain and related outcomes, such as mood, anxiety, sleep, and fatigue. Results from the study will inform future research on psychological interventions for chronic pain and contribute to understanding the psychological change processes involved in improvements in chronic pain.

Risk/Benefit Ratio:

The risks of this study are small. We will be gaining valuable information to help improve our understanding of the psychological processes involved in improvement in chronic pain and help inform research aimed at using alternate psychological treatment strategies for older adults with chronic pain.

Alternatives to Participation:

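### For a participant on site with suicidal or violent ideation, Section 6.0 says immediate emergency referral in one place and evaluation first, with the ER only if hospitalization is judged necessary, in another

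*Combined protocol and SAP*

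**What the plan says.** Section 6.0 of the combined protocol and SAP deals with suicidal or violent ideation twice.

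The first place is the safety-monitoring text under Risks and Risk Minimization. It sets up a verbal check-in at the start of every therapy session and a telephone route between sessions. The paragraph on what staff then do begins "On check-in or upon receiving a phone call from the participant" and says: "In the event of suicidal or violent ideation, the participant will be referred immediately to the emergency department or to 911". It gives no evaluation step and no condition. The same sentence presents the rule as that of the later plan: "as outlined in our suicide safety plan below".

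The second place is the Suicide Safety Plan itself, which splits by setting. For a participant on site the trigger is: "If researchers feel that the participant is at risk for suicide and/or a threat to others while he/she is present at WLA". The action has two steps. First, "he/she will be evaluated by a trained research physician or psychologist who is a study team member". Then the participant is "brought to the WLA ER if psychiatric hospitalization is thought to be required". For a participant who is not at WLA, the plan says that Veterans will be "instructed to dial 911 or report to the nearest ER if a psychiatric emergency, such as suicidal or violent ideation, occurs during the study".

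**The concern.** A therapist who hears a disclosure at check-in and reads the monitoring text refers the participant to emergency care at once. If the therapist follows the pointer to the plan, the on-site rule there is different: a named type of clinician evaluates, and the ER depends on that clinician's view about hospitalization.

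This matters because the protocol itself justifies having a plan by the doubled suicide rate among people with chronic pain. The person who hears the disclosure may also not be one of the evaluators the plan names. Section 5.6 allows trainee interventionists to be social workers or marriage and family therapists, and to run sessions independently after shadowing. Such a therapist has to know whether to refer directly or to call a study physician or psychologist. Finally, Section 6.0 requires protocol deviations to be reported immediately to the IRB, and with two texts it is unclear which one a deviation is measured against.

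**Working it through.** No arithmetic applies, and the plan gives no figure to reproduce. The check is to set the two texts side by side by setting, trigger and action.

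| Situation | Monitoring text (Risks and Risk Minimization) | Suicide Safety Plan | Do they agree? |
|---|---|---|---|
| Off site, ideation | Immediate referral to the emergency department or 911 | 911 or nearest ER, no condition | Yes |
| On site, ideation, hospitalization judged necessary | Immediate referral | Evaluation by study clinician, then WLA ER | Same end point, different order |
| On site, ideation, hospitalization not judged necessary | Immediate referral | Evaluation; ER not called for | No |

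**Step 1: which setting does the check-in belong to?** The check-in opens each therapy session, and Section 4.0 places all study procedures at WLA. A disclosure at check-in therefore falls under the plan's on-site branch. A call from a participant who is away from WLA falls under the off-site branch.

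**Step 2: off site.** The plan's off-site sentence names suicidal or violent ideation as an example of a psychiatric emergency and sends the participant to 911 or an ER without condition. That matches the monitoring text in both trigger and action.

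**Step 3: on site, triggers.** The monitoring text acts on ideation. The plan's on-site branch acts on the researchers' feeling that the participant is a suicide risk or a threat to others. These are not the same test. A participant may disclose ideation without being felt to be at risk. Read literally, the monitoring text then requires referral, and the plan's on-site branch is not reached.

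**Step 4: on site, actions.** Where the plan's branch is reached, evaluation comes before any transfer, whereas the monitoring text requires referral immediately. If the evaluator thinks hospitalization is needed, both routes end at the ER. If not, the monitoring text still requires emergency referral and the plan does not. The plan then gives no further instruction for that participant: its closing sentence covers significant depression in someone who is not suicidal.

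**Step 5: does the cross-reference resolve it?** It would if the plan contained the rule attributed to it. For a participant on site, it does not contain an unconditional referral. The pointer therefore leads to a different instruction.

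**The case against.** The best defence is that the monitoring text defers expressly to the plan, so it can be read as a short summary with the plan as the operative procedure. The plan does not forbid emergency referral after evaluation, and the differing triggers may mean that the two sentences were written for different levels of concern. The situation may also be rare: Section 5.4 excludes active suicide or violence risk in the past 6 months, and the plan states that no participant is expected to develop suicidal ideation.

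Part of this stands. It limits the problem to the on-site case, and it means that a reader who infers that staff can never satisfy both texts goes too far. It does not remove the mismatch. A summary should not state an unconditional rule where its source states a conditional one, and nothing in the text says that the plan prevails. Rarity bears on how often the question arises, not on whether the instruction is clear when it does.

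Two stronger readings are tempting, and the documents support neither.

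- **A conflict over suspending treatment.** The monitoring text says: "In the event of suicidal or violent ideation, study procedures (i.e., psychotherapy) will be suspended immediately". The plan does not mention suspension. Silence in one place does not contradict a clear rule in the other.
- **Different handling by arm, and so bias.** Each interventionist delivers only one treatment (Section 5.6), so a reader might infer that differing interpretations would line up with arm. However, the same check-in opens sessions in both arms, and the plan assigns the evaluation to a study physician or psychologist, not to the arm's therapist as such. Nothing in the documents suggests that the two arms would read the text differently.

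**Conclusion.** The inconsistency is real and confined to participants on site. There, Section 6.0 states one trigger and an immediate, unconditional referral in the monitoring text, and another trigger with evaluation first and a conditional ER transfer in the plan. The required action differs when ideation is present and hospitalization is not thought necessary; when hospitalization is thought necessary, only the sequence differs.

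This conclusion rests on reading both texts literally and on check-ins taking place at WLA, as Section 4.0 indicates. The frequency of the divergent case cannot be estimated from the documents. This is a wording contradiction in a safety procedure, with no bearing on sample size, power or the analysis plan. It should be corrected because it concerns participant safety and costs little to fix. Which rule is right is a clinical matter and is not judged here.

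**What to change.** Replace the two on-site statements with one instruction that has a single trigger and a single sequence of steps. Use the same text in the monitoring section and in the Suicide Safety Plan, so that the cross-reference points to what it describes. The instruction should say explicitly what applies to a participant on site who has ideation but is not thought to need hospitalization, since that is where the present texts part. The study's clinicians and the IRB must decide which rule stands. The off-site wording already agrees and need not change for this purpose.

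The cost is protocol wording and a minor IRB amendment. Assessments, sample size and analysis are unaffected.

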7.0 Privacy and Confidentiality

Taking part in this study will involve collecting private information about participants, including name, diagnoses, medications, responses to study questionnaires, and video recordings. All information will be labeled with an alphanumeric code to protect participant confidentiality. Study records will be stored in a locked cabinet in [name] or [name]. See below for further information on data security.

Information about participants will be combined, publications and presentations about the combined data we have gathered will be created. Any talks or papers about this study will not identify individual participants.

In addition, a description of this clinical trial will be available on <http://www.ClinicalTrials.gov> as required by U.S. Law. This website will not include PHI for study participants. At most, the website will include a summary of the results.

We will not share participant records or identify participants unless we are legally required. Participants will be notified that the following government agencies may have access to their records: Office of Human Research Protections, the Government Accountability Office, the Office of the Inspector General, the VA Office of Research Oversight, the VA Greater Los Angeles IRB, our local Research and Development Committee, the sponsor (VA Clinical Science Research and Development – CSR&D), and the CSR&D Data Monitoring Committee.

By law, information can still be released if we find or suspect child abuse, elder abuse, an by a participant intent to harm him/herself or others, or if a participant has an infectious disease that State or Federal law requires us to report.

Participants are permitted to release data about themselves or involvement in the study.

8.0 Communication Plan

Data Security Plan:

At the time of a patient's enrollment, appropriate informed consent is obtained, and all prior identifying information obtained during screening is destroyed. Each participant has a hardcopy of the original signed consent form. A study folder for each participant is created with an alphanumeric code that does not include portions of the participant's social security number. These folders contain completed questionnaires and data sheets with corresponding labeling by alphanumeric code. The decoding algorithm is stored in a password protected encrypted electronic file. Hardcopy study folders are stored in a locked filing cabinet in the locked office of the PI (WLA, [name]). The PI has primary access to the key to the filing cabinet where hardcopy records are kept. Other project staff (Study Coordinator, investigators, and assistants) have access to the hardcopy records only through the PI.

For video files of psychotherapy sessions, a customized VA intranet-based data system is created. Data are collected and processed on a separate VA laptop computer, and the files are extracted and uploaded into the primary database. The system is housed on the VAGLAHS Geriatric Psychiatry research server. An alphanumeric code is generated for all video files. All files are encrypted, and the systems and tools are protected by 128-bit SSL, the secure socket layer technology used for sensitive transactions on the web. The system is accessible only via the VA intranet and employs a hierarchical system of password protected logins, allowing differential access to project team members as appropriate to their roles. Data are accessed only through the system, not transported. [name] (Co-Investigator) and his team have extensive experience conducting and

supporting studies ranging from small pilot studies to large multisite centers, which have required creating data systems such as this for neuroimaging data and other types of encrypted electronic files.

Data Banking/Future Use:

Participants will be invited to have their data (interviews, questionnaires, and video recordings of psychotherapy sessions) stored in a new repository after study closure for future research involving psychotherapy, aging, psychological processes, and chronic pain; this will be optional for participants. Prior to study closure, an application for the creation of a new data repository will be submitted to the local IRB. Information will be labeled with a code that does not contain participants name or other ways that identify them. Any future research will be done for research purposes only; participants' doctors will not be notified about the results of the research.

Privacy Breaches:

In the event of a privacy breach, the IRB and involved participants will be notified immediately, in accordance with IRB policy.

